### **Study Design:**

**Study population:** Consecutive patients with vision problems who have been diagnosed with Wet-AMD attending SOC eye clinics will be recruited in the study after meeting the inclusion and exclusion criteria.

### **Inclusion Criteria:**

1. Participants between ages 21 and 100
2. Both genders
3. Subjects with maculopathies
4. Ability to comply with the study protocol, in the investigator's judgment
5. Subjects must have the cognitive capacity to provide personal consent (i.e. no cognitively impaired persons will be recruited).

### **Exclusion Criteria:**

1. Uncontrolled blood pressure, defined as systolic blood pressure >180 millimeters of mercury (mmHg) and/or diastolic blood pressure >100 mmHg while a patient is at rest.
2. Any concurrent intraocular condition in the study eye that, in the opinion of the investigator, could either reduce the potential for visual improvement or require medical or surgical intervention during the study.
3. History of idiopathic or autoimmune-associated uveitis in either eye.

4. Active ocular inflammation or suspected or active ocular or periocular infection in either eye.
5. Other protocol-specified exclusion criteria may apply.
6. Individuals with indications of cognitive impairment and unable to make decisions for themselves to provide informed consent will be excluded from the study.

**Study Procedure:**

This cohort study will involve 1 study visit.

**Pre-specified clinical outcome:** The prespecified adverse clinical outcome used in this study will be the **maculopathy** which will be identified by an increase in central retinal thickness (CRT) of at least 100 microns or a loss of best-corrected VA of 5 letters or more.

Clinical Validation will be a cohort study design to evaluate the diagnostic accuracy of the CRYSTALSIGHT device compared to the Tobii gaze-tracker in patients with macular diseases recruited from the medical retina specialty clinic.

This study will be conducted in accordance with the tenets of the Declaration of Helsinki.

The goal is to recruit a minimum number of 20 patients with diagnosed indication of maculopathies who fit the inclusion and exclusion criteria. Adult individuals will be voluntarily recruited from Tan Tock Seng Hospital (TTSH) Ophthalmology SOC clinics after they had been assessed for eligibility based on established clinical diagnosis from the case notes through TTSHs NGEMR. Informed consent for participation in this study will be obtained. Eye gaze tracking test will be automated, and patients will only need to follow through the stimulus/image shown without physical contact with the eye gaze tracker using CRYSTALSIGHT and Tobii. A series of stimulus dots in the form of a pursuit (moving stimulus) or saccade (fixed stimulus and fixed speed) will be presented on the screen and the user under test (UAT) will need to look at the targets presented. The test is similar to Microperimetry and Humphrey's visual field test. A score will be generated at the end of the test.

A research collaboration agreement was established between TAN TOCK SENG HOSPITAL PTE. LTD. and OCCUTRACK MEDICAL SOLUTIONS PTE LTD on the research project titled: CRYSTALSIGHT: "Cohort 1.5" clinical investigation study with OCCUTRACK and Tan Tock

Seng Eye Clinic to further develop remote monitoring of age-related macular degeneration at home using artificial intelligence for eye tracking.

Research Procedures:

**1) CRYSTALSIGHT**

**2) Tobii**

Subjects perform the CRYSTALSIGHT test monocularly and pursue a pre-determined target moving in a customized waveform across the computer screen. The trail of the gaze points generated by the subject following the target is simultaneously recorded and stored. Eye dilation will not be required for the purpose of this research study as fundoscopy nor OCT imaging will not be performed.

As part of the clinical evaluation of subjects during the analysis phase, access and extraction of data will be limited to TTSH's NGEMR and Heidelberg Eye Explorer platform. Clinical information collected for the purposes of this study would include current diagnosis, co-morbid information e.g DM, hyperlipidemia, and hypertension histories along with prior visual assessments documented by optometrists as well as recent OCT imaging.

In addition, this is also to note that NEHR cannot and will not be used for research. Assess of medical records for the purpose of data collection will also be limited to the period dated from 1 March 2025 to 28 February 2026. Clinical information/data collected will be done once off during, or retrospectively after the study visit.

**Measurements at Baseline (Day – 1)**

The following variables will be collected at initial baseline visit.

- Demographic data (age, gender)
- Phenotypic risk factors such as drusen and pigment abnormalities
- Smoking status
- Co-morbidity status such as diabetes, Cancers, CVD, strokes, kidney diseases
- Drugs history (Eye related)
- Drugs history (Co-morbidity status)
- Eye measurements:
  - o CRYSTALSIGHT

- AVIGA
- BCVA (Best Corrected visual acuity)

## Sample size calculation

The sample size calculation is based on the intraclass correlation between CRYSTALSIGHT and Tobbi. Our minimum acceptable intraclass correlation coefficient (ICC) is 76% between CRYSTALSIGHT and Tobbi, and the expected ICC is 93%, basing on two- sided significance level of 0.05 and power 0.8, a total of 20 subjects are required. Statistical analysis to assess the eye-tracking performance of CRYSTALSIGHT, will be applied through the following methods:

- The Bland and Altman plot will be used to assess the agreement between CRYSTALSIGHT and Tobbi. The difference between CRYSTALSIGHT and Tobbi of each subject will be plotted on the vertical axis, again, the mean of the two readings of each subject on the horizontal axis. Limits of agreement will be presented in the plot.
- Intraclass correlation Coefficient will be computed using a random effect model, including device type (CRYSTALSIGHT vs. Tobbi) as a fixed factor and subject as a random effect. This model accounts for variability between subjects while assessing agreement between the two devices.

In literature, gaze-tracking accuracy measures such as K-means clustering and Euclidean distances were used and will be evaluated for suitability [35, 36]

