## 2. STUDY DESIGN

The development of a next-generation 'CRYSTALSIGHT' solution using combinations of a novel and cost-effective eye-tracking system with artificial intelligence-based eye-tracking algorithms that detect macular abnormalities and enable clinicians to review and monitor the prognosis of patients via a web platform through the following deliverables.

- a. Evaluate and improve a home-monitoring regimen involving the self-tests of the CRYSTALSIGHT gaze-tracking system.
- b. To demonstrate that CRYSTALSIGHT has the same or superior gaze-tracking capacities as Tobii.
- c. Evaluate the CRYSTALSIGHT device for its functionality and ease of use as a qualitative measurement tool for patients.
- d. Develop the Design History File (DHF) for regulatory filing requirements.

2. This study will improve on the existing gaze-based scoring methodology for disease activity monitoring over time (delta-change) by quantitatively measuring saccadic speed, pursuit and micro-saccades.

Validation of the machine learning algorithm has been completed with an accuracy of xxx > 85% against gold standard test. The Gold Standard Tests used in this validation of the machine learning algorithm are standard visual acuity (VA) and central visual field (VF) test, which are currently used in standard routine clinical practice.

Using fixation data, the accuracy is 0.91, the sensitivity and specificity are 0.76 and 0.95, respectively. Using smooth pursuit, the accuracy is 0.92, the sensitivity and specificity are 0.82 and 0.95, respectively.

TABLE I  
THE RESULT OF IMPAIRED VISION DETECTION.

	Fixation	Pursuit
accuracy	0.91	0.92
sensitivity	0.76	0.82
specificity	0.95	0.95

The hypothesis of this study is to show that a person's visual performance can be assessed non-invasively and from the comfort of their home, without the need for manual or expert intervention, by utilizing the newly developed 'CRYSTALSIGHT' device. A previous study

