utilized a commercial gaze-tracker "Tobii ET5L", the hypothesis of this study establishes that the CRYSTALSIGHT eye tracking device has comparable non-inferior performance to the commercial camera and generates an objective score while minimizing patients' need to interact with the machine. Tobii ET5L is an infrared gaze-tracking camera, whilst CRYSTALSIGHT is a video-based camera. The quantitative outcome of the study may enable the clinical trial team to determine that the CRYSTALSIGHT device performs with acceptable or similar performance metrics to the commercial device, which provides an indicative score for disease activity in patients with maculopathies. The findings of this study could also potentially show that the CRYSTALSIGHT device may be used in a home-based setting to determine macular disease activity over time.

Previous studies have shown the potential of gaze tracking to provide an objective score with relevant diagnostic assistance information while minimizing patients' need to interact with the machine.

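### Deliverable (b) is to show the same or superior gaze tracking, but the fixed analyses measure only agreement on an unnamed reading, and the gaze-error measure is left open

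*Protocol*

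**What the plan says.** **Aim.** Protocol, 2. STUDY DESIGN, deliverable (b): "To demonstrate that CRYSTALSIGHT has the same or superior gaze-tracking capacities as Tobii". The hypothesis in the same section is that the "CRYSTALSIGHT eye tracking device has comparable non-inferior performance to the commercial camera and generates an objective score". No non-inferiority margin accompanies either statement.

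**Data.** The Study Procedure says "A score will be generated at the end of the test", without defining the score. Under Research Procedures the patient follows a moving target whose path is set in advance, and "The trail of the gaze points generated by the subject following the target is simultaneously recorded and stored".

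**Analysis.** The Sample size calculation section lists the methods for assessing eye-tracking performance. One is a Bland-Altman plot of the within-subject difference against "the mean of the two readings of each subject on the horizontal axis". The other is an ICC from a model with device as a fixed factor and subject as a random effect. The study is sized on that ICC: "Our minimum acceptable intraclass correlation coefficient (ICC) is 76% between CRYSTALSIGHT and Tobbi", and "the expected ICC is 93" percent. The section does not say which variable the reading is and gives no acceptable limits of agreement. Its last sentence says that in the literature "gaze-tracking accuracy measures such as K-means clustering and Euclidean distances were used and will be evaluated for suitability".

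**The concern.** A claim of equal or better tracking needs a quantity that says how far recorded gaze lies from where the target was, and a comparison with a direction. The two fixed analyses have neither, unless the unnamed reading happens to be such a distance. The measure that would answer the question can be computed, because the target path is known and the gaze trail is kept, yet it is the part left undecided. It is listed beside K-means clustering under the label of an accuracy measure, although the spread of points around their own cluster centres says nothing about the target.

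At stake is what the study can conclude. A high ICC could be reported as meeting deliverable (b) when it shows only that two readings rank and space patients alike. A reader of the protocol cannot tell which result would establish (b) and which would refute it.

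**Working it through.** **1. The plan's own figure.** Inputs from the Sample size calculation section: null ICC 0.76, expected ICC 0.93, two-sided alpha 0.05, power 0.80, and k = 2 readings per subject. The Walter-Eliasziw-Donner formula is

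n = 1 + 2k(z_α + z_β)² / [(k − 1)(ln C₀)²], with C₀ = (1 + kθ₀)/(1 + kθ₁) and θ = ICC/(1 − ICC).

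- θ₀ = 0.76/0.24 = 3.167 and θ₁ = 0.93/0.07 = 13.286
- C₀ = 7.333/27.571 = 0.266 and ln C₀ = −1.324
- n = 1 + 4 × (1.960 + 0.842)²/1.754 = 18.9, so 19

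The exact F test at alpha/2 gives 20, with power 0.80 to 0.81. The stated 20 reproduces, so the problem is what is measured, not the arithmetic.

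**2. What an ICC of 0.93 says about each device.** Set the between-subject variance to 1 and let the device error variances be c² (CRYSTALSIGHT) and t² (Tobii). With no mean offset, ICC = 1/[1 + (c² + t²)/2]. An ICC of 0.93 fixes only the sum: (c² + t²)/2 = 1/0.93 − 1 = 0.0753.

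| Error SD, CRYSTALSIGHT | Error SD, Tobii | ICC |
|---|---|---|
| 0.27 | 0.27 | 0.93 |
| 0.39 | 0 | 0.93 |
| 0 | 0.39 | 0.93 |

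Simulation with 20,000 subjects gave 0.929 to 0.930 in all three cases. The same result fits CRYSTALSIGHT as the worse tracker, the equal or the better.

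**3. A fixed device offset.** The section makes device a fixed factor but does not say whether its effect enters the ICC denominator. For an offset of b between-subject SDs, the consistency form stays at 0.93. The absolute-agreement form is about 1/(1 + 0.0753 + b²/2).

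| Offset b | Consistency ICC | Absolute-agreement ICC (simulated) |
|---|---|---|
| 0 | 0.93 | 0.93 |
| 0.5 | 0.93 | 0.83 |
| 1 | 0.93 | 0.63 |
| 2 | 0.93 | 0.32 |

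The Bland-Altman plot would reveal such an offset in the readings, but not which device is nearer the target.

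**4. K-means.** Assumed layout: five fixed targets, 100 gaze points each, noise SD 0.5 units per axis, and a constant horizontal shift.

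| Shift | Within-cluster mean square | Mean distance to true target | Cluster centre to true target |
|---|---|---|---|
| 0 | 0.484 | 0.62 | 0.06 |
| 3 | 0.484 | 3.04 | 3.00 |

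Dispersion does not see the shift, because centres and points move together. Both distances to the true target do.

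**5. What 20 patients could show on gaze error.** The protocol gives no margin and no SD, so only a range is possible. Assume a paired non-inferiority t test, one-sided 2.5%, power 0.80 and no true difference. Margins of 0.3, 0.5, 0.75 and 1.0 SD of the paired difference need 90, 34, 16 and 10 patients. With 20 patients the margin must be at least about 0.66 SD.

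**The case against.** **The choice of metric may belong in a statistical analysis plan that is not shown.** This holds for computational detail. It does not cover an aim and a list of methods that fail to meet within the protocol itself.

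**Agreement does bear on comparable performance.** It does, and the planned analyses can support similarity of readings. They cannot support superiority, and an ICC floor of 0.76 is not a margin on tracking error.

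**The unnamed reading might already be a gaze-to-target distance.** Then the Bland-Altman mean difference would have a direction and would go some way towards (b), while the ICC still would not. The open last sentence makes this unlikely but does not exclude it, which is why the reading must be named.

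**Gaze-to-target distance is itself impure in these patients.** This stands. Macular disease can shift fixation off the target, so the distance mixes patient and tracker error. Assume noise SD 0.7 degrees and fixation 3 degrees off target. An accurate tracker then shows a mean error of 3.08 degrees, and one with a 2-degree offset in the opposite direction shows 1.28 and looks better. With fixation directions random across patients, the 2-degree offset moves the mean from 3.08 to 3.44: the right way, but only slightly.

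A reader might also infer stronger points that the documents do not support:

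- *The reading is the end-of-test score and mostly reflects vision.* The score is the only numeric test output described, but nothing links it to the ICC, and its content is undefined.
- *The metric will be picked after seeing the data.* The sentence gives no timing.
- *K-means can never show accuracy.* Centres compared with known targets detect an offset, and Euclidean distance is listed beside it.
- *The false-positive rate is inflated by trying several metrics.* No test or success rule is attached to these measures.

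**Conclusion.** The point holds as a mismatch between aim and analysis. The fixed analyses can show that two readings agree. Unless the reading proves to be a distance to the target, they cannot show that CRYSTALSIGHT tracks as well as or better than Tobii. The symmetry of the ICC is algebraic and rests on no assumed value. The insensitivity of within-cluster dispersion to a constant offset is likewise general while clusters stay separable; the figures 0.484, 0.62 and 3.04 belong to the assumed layout with accurate fixation.

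How large a tracking deficit could go unnoticed cannot be stated, since the protocol gives no gaze-error SD, margin or acceptable limits. The sample size is correct for the ICC question it addresses. The change should be made, but it does not invalidate the study as a study of agreement.

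**What to change.** Before any gaze data are scored:

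1. Name the reading used in the ICC and the Bland-Altman plot.
2. Replace the last sentence of the Sample size calculation section with:

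> Gaze-tracking error is the mean Euclidean distance between recorded gaze and displayed target position, per patient and device, from the stored gaze trail. For deliverable (b) the paired difference CRYSTALSIGHT minus Tobii is reported with its 95% CI and a Bland-Altman plot, together with the signed horizontal and vertical between-device offset. K-means dispersion is descriptive of gaze stability only.

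3. Either state a non-inferiority margin in advance, or reword deliverable (b) as estimating the difference between devices.

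**Cost.** Protocol wording and modest extra analysis, with no new patients or visits. It requires the trail to be stored for both devices; the protocol states storage once, in describing the CRYSTALSIGHT test, so this should be confirmed for Tobii. A margin tighter than about 0.66 SD of the paired difference would need more than 20 patients for 80% power.

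**Limitation to state.** With eccentric fixation the error includes the patient's own fixation error. It should be read as a paired between-device difference, beside the signed offset, and not as absolute tracker accuracy.
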